#### 3.2 Target Population and Number of Volunteers

The target population for this study is adult male and female volunteers. The study requires up to 400 volunteers (200 completers) successfully complete the study to run statistical analyses. We anticipate up to 50% drop-out between study session 1 and 2 as attrition is high in MTurk populations (Mason and Suri, 2012). A “completer” is defined as completing the HBMT with at least 60% of the stems completed correctly and participating at both T1 and T2.

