#### 3.3 Study Design, Methodology, and Experimental Manipulations

The study consists of a two group design. Assignment to each of the two experimental conditions is determined randomly upon the volunteers’ arrival to the study webpage. However, the website will be programmed to achieve equal sample size across the two groups. The duration of participation for each volunteer is estimated to be about 60 minutes (total, including both time-points). Volunteers will complete the following as part of the study:

- a. HBMT: Volunteers will complete a computer-based hostile bias modification training where they are instructed to complete word fragments (words with missing letters) to form non-aggressive words. The word fragments are based on similar stimuli used in prior research on hostile bias (Anderson, Carnagey, & Eubanks, 2003; DeWall & Bushman, 2009). This task was validated in a previous study (WRAIR # 2574).
- b. Angry Cognitions Scale/HAB measure: This measure asks respondents to read hypothetical scenarios and indicate how they would interpret and respond to them. It was developed by Martin and Dahlen (2007) and will be used as a measure of HAB.
- c. Trait anger Scale: Brief measure of trait anger validated by Wilk et al., (2015).
- d. State Aggression Survey: This survey is adapted from several others in the literature to measure variance along the normal spectrum of aggressive behaviors in daily life that the average person might display (Álvarez-García, et al., 2016; Deffenbacher, et al., 2001; Deffenbacher, J. et al., 2002). The survey specifically asks about driving behaviors (e.g., yelling at other drivers), and public online behaviors (e.g., posting mean comments on social media), as well as generic public displays of aggression items (e.g., Gotten angry and slammed a door).

- e. State Emotion Survey: A short measure of state (current or recent) emotions over the preceding 24 hour period adapted from Goldberg et al., (2006) and Quartana and Burns (2007).
- f. Demographic questions: Volunteers will be asked to provide their age (whole number, not birth date), highest level of education, and gender. These will be used as statistical controls in analyses.

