## 9 STATISTICAL METHODS AND DATA ANALYSIS

### 9.1 Analyses for Main Study Hypotheses

Between group differences (comparing real vs. fake HBMT) in the change in state anger and state HAB across time points (change from time-point one to time-point two) will be primarily assessed with a mixed-designs ANOVA. Between group differences in state aggression measured at time-point two will be assessed with a General Linear Models (GLM) analysis controlling for trait anger and demographics (age and gender).

We will also plot effect of group comparing real vs. fake HBMT and time between time-points (24-96 hours) on change scores (time 2 anger/aggression minus time 1 anger aggression) and analyze this using a linear regression with an interaction term.

Lower order effects will be tested using corrected Fishers LSD, Tukey, Scheffe, or other pairwise test as appropriate. Appropriate data-transformations may be used as necessary to satisfy significance test requirements. Lower order effects will also be assessed with pairwise dependent means t-tests. Age and gender will be controlled as covariates. Mediation analyses (if used) will be performed using non-parametric Monte-Carlo bootstrapping procedures using PROCESS (see Hayes, 2017).

We may use age, gender, and trait measures as control variables in analyses.

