### 9.2 Level of Significance to be used

Determination of statistical significance for all analyses will be  $\alpha = 0.05$ . In the case of directional significance tests (e.g., tests using t-distributions), one-tailed tests will be used for *a-priori* directional hypotheses (Section 5.1) and two-tailed for non-directional hypotheses and *post-hoc* hypotheses).

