### **9.4 Accounting for Missing, Unused, and Spurious Data**

Missing data will be identified as such in the database and will not be imputed or replaced for analytic purposes. Little's Missing Completely at Random (MCAR) test (Little, 1988) will be used to confirm that all missing data were missing "completely at random". Participants with small amounts of missing data ( $\leq 15\%$ ) will be excluded from analyses pairwise, whereas volunteers with large amounts of missing data ( $>15\%$ ) will be excluded listwise. Outliers are defined as individual scores that fall beyond an acceptable range (1.5 inter-quartile ranges above the third quartile or below the first quartile). Outliers will be identified as such in the database, and will not be included in data analyses, or will be transformed as appropriate for use in the data analytic strategy.

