### **9.5 Procedures for Reporting Deviations from the Original Statistical Plan**

Any deviation(s) from the original statistical plan will be described and justified in a protocol amendment and/or in the final report, as appropriate.

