#### **10.6 Financial Incentives to Volunteers**

Volunteers will be paid up to \$5 for their participation in this study. All volunteers who complete time-point one of the study will receive \$3 and volunteers will receive an additional \$2 if they complete time-point two of the study. This rate is standard pay for MTurk work (See Hitlin, 2016). Most MTurk tasks pay 10 cents or less and result in less than an equivalent hourly wage of \$5. Volunteers will not be paid for participation in a time point if they do not complete an entire time point (i.e., progress through each activity/survey and reach the end screen; volunteers may skip any question they do not wish to answer on surveys without affecting payment). If a volunteer is terminated from the study as a result of website, server, or study program related failures (e.g., server goes down during study), they may request payment by contacting the PI directly. The PI will ask Volunteerscience.org to verify that the server/website failure had occurred and if so to pay the volunteer. The approval authority of such requests is the PI. Volunteerscience.com will track the performance of each volunteer using their MTurk handle and calculate compensation appropriately without sharing any PII (including MTurk handle) with ARL or WRAIR staff.

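### Section 9.4 lets valid high aggression scores be deleted or transformed on a 1.5 IQR fence alone, with the reference set, score level and choosing rule left open

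*Combined protocol and SAP*

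**What the plan says.** Section 9.4 has one test for an outlier: "Outliers are defined as individual scores that fall beyond an acceptable range (1.5 inter-quartile ranges above the third quartile or below the first quartile". Scores that meet it are marked in the database and then "will not be included in data analyses, or will be transformed as appropriate for use in the data analytic strategy". No check that the score is an error is required. The multiplier is fixed. Four things are not:

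- whether the quartiles come from both arms together or from each arm;
- whether the score is an item or a total;
- which transformation is meant;
- what decides between deleting and transforming.

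No other section settles these. Section 9.1 adds a second opening: "Appropriate data-transformations may be used as necessary to satisfy significance test requirements". Section 9.6 only points back to 9.4. Section 9.5 provides that "Any deviation(s) from the original statistical plan will be described and justified in a protocol amendment and/or in the final report", but deleting and transforming both comply with 9.4, so neither would count as a deviation. No analysis with all scores kept is planned.

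State aggression is part of Hypothesis 1 (5.1). It is compared at time-point two in a GLM with trait anger, age and gender (9.1). Appendix F has 2 general, 7 online and 12 driving items, 21 in all, each a past-24-hour frequency from 1 (never) to 5 (five or more times). Section 3.3 says the survey is meant "to measure variance along the normal spectrum of aggressive behaviors in daily life that the average person might display".

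**The concern.** A fence of this kind is a screening device. It marks scores that are unusual relative to the middle half of the sample; it does not show that they are wrong. On a bounded frequency scale, a volunteer who reports many aggressive acts in a day may be answering truthfully, and the survey is there to record that. If training works by reducing aggression in proportion, the upper tail is where the arms differ most, and deleting it removes part of the effect.

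The second problem is the open choice. An analyst could see results by arm, then choose deletion or a transformation, pooled or per-arm fences, items or totals, and remain within the plan. At stake are the power and the false-positive rate of one component of the primary hypothesis.

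**Working it through.** **Inputs from the plan.** d = .4, 80% power, 100 completers per arm (7.2); alpha .05, one-tailed for directional tests of the 5.1 hypotheses (9.2).

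**The plan's own figure.** Two-sided, n per arm = 2(1.96 + 0.8416)² / 0.4² = 98.1, so 99 per arm or 198 in total, in line with the stated 200. At 100 per arm, power is 80.7% two-sided and 88.2% one-sided (normal approximation).

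**Share flagged by shape alone.** Normal: Q3 = 0.6745 SD and IQR = 1.349 SD, so the fence is 0.6745 + 1.5 × 1.349 = 2.698 SD and 0.7% are flagged over both tails. Exponential: the fence is ln 4 + 1.5 ln 3, so the share is 1/(4 × 3^1.5) = 4.8%, all in the upper tail.

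**If the rule is applied to items.** For any item that fewer than 25% of volunteers report, Q1 = Q3 = 1, IQR = 0 and the upper fence is 1 + 1.5 × 0 = 1. Every report of that behaviour is then an outlier.

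**Simulation 1: totals, with the GLM covariates.** The distribution is assumed: gamma-distributed propensity, Poisson item counts recoded 1–5, unweighted 21-item sum, non-drivers scored 1 on driving items, 60–100% driving. Rate ratios of .42–.72 were calibrated to d = .40. Trait anger was assumed to correlate about .5 with propensity. There were 2,000 trials per cell, and power is one-sided.

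| Fake arm at floor | Removed by pooled fence, fake / real | d, all kept → after deletion | Power: all kept | Power: pooled deletion | Power: log, all kept | False positives, per-arm fences |
|---|---|---|---|---|---|---|
| 4% | 5.2% / 1.4% | .40 → .34 | .93 | .83 | .88 | .10 |
| 11% | 7.7% / 2.2% | .39 → .30 | .92 | .74 | .85 | .13 |
| 22% | 9.0% / 2.6% | .40 → .28 | .91 | .66 | .86 | .15 |
| 28% | 11.0% / 3.2% | .41 → .26 | .94 | .62 | .89 | .16 |
| 41% | 13.2% / 4.3% | .40 → .24 | .93 | .54 | .90 | .21 |
| 51% | 16.5% / 6.3% | .40 → .21 | .94 | .46 | .92 | .18 |

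The number left after deletion runs from 200 − 5.2 − 1.4 = 193 to 200 − 16.5 − 6.3 = 177. One-sided false positives are 5.1–5.3% for pooled deletion, and 7.1–8.4% if the better of pooled deletion or log is picked. A further run on similar assumptions gave .90–.93 with all kept, .46–.75 with pooled deletion and 11–18% false positives with per-arm fences.

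**Simulation 2: independent, no covariates.** Total = 21 + gamma-Poisson count, capped at 105; 10,000 runs per shape; one-sided.

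| Skewness | All kept | Pooled deletion | Set to pooled fence | Log | False positives, per-arm fences |
|---|---|---|---|---|---|
| 1.4 | 89% | 75% | 88% | 83% | 10.7% |
| 2.0 | 89% | 66% | 88% | 81% | 13.2% |
| 2.8 | 91% | 50% | 86% | 83% | 17.1% |
| 3.9 | 94% | 27% | 83% | 89% | 22.7% |

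All kept, pooled deletion, set-to-fence and log, each fixed in advance, hold false positives at 4.7–5.2%. Per-arm fences do not, because each arm's cut-off moves with its own tail and the test takes no account of that.

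**Shapes that point the other way** (unadjusted t-test, 4,000 trials). Near-normal: power .88 to .86 after pooled deletion. Lognormal with a pure location shift: .87 to .997.

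**Careless answers.** If 3% give one answer of 3–5 throughout (assumed), power in simulation 1 is .20–.51 with all kept unaltered, .52–.83 with pooled deletion and .73–.79 with log. In the further run, setting to the fence gave .81–.83 against .71–.74 for log.

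**The case against.** The best defence is that a fence protects against careless answers from an online panel. The figures bear this out: with 3% careless responders, keeping everything unaltered is the worst of the options compared. The defence supports having a rule, but not leaving it open or deleting in-range scores in the main analysis. It is also fair that transforming outliers can be read as pulling them in to the fence, which performs well. The plan may therefore already permit a good rule; it does not commit to it. Marking outliers in the database keeps a reanalysis possible, but does not say which result counts.

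Some stronger readings are tempting, and the documents do not support them:

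- **That false positives in this trial will be 10–21%.** This needs per-arm fences, which the text neither states nor excludes. Pooled deletion fixed in advance keeps them near 5%.
- **That power will fall to .46, or lower.** This needs about half the fake arm at the floor and a rate ratio near .42. No score distribution is given, and other shapes show a trivial loss or a gain.
- **That most reports will be discarded as outliers.** This needs the item-level reading, which is possible but not stated.
- **That the plan has no other data-quality provision.** Besides the completer criterion in 3.2, 9.4 excludes volunteers with more than 15% missing data, 7.2 asks for completers who follow the task instructions, and 11.9.3 lists data cleaning. None is described as a check for careless survey answers.
- **That a log analysis is required.** It is one acceptable choice among several.

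No problem is shown here for state anger or HAB.

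**Conclusion.** The gap in the text is certain: in-range aggression scores can be removed on a fence alone, and the choices around that rule stay open within the plan. Its consequence is conditional. With right-skewed totals, a proportional effect, d = .40 and 100 per arm, pooled deletion takes one-sided power from about .90–.94 to about .83–.46 with the planned covariates, at a false-positive rate near 5%. Per-arm fences would bring about 10–21% one-sided false positives, and picking the better of pooled deletion or log afterwards 7–8%. Near-normal scores would make the matter minor, and a pure location shift would reverse the direction for power. These are ranges over assumed shapes, not estimates for this trial. It should be fixed before analysis, because a rule the plan allows can weaken or distort part of the primary hypothesis and the remedy is a change of wording.

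**What to change.** For the state aggression outcome only, replace the delete-or-transform sentence in 9.4 with:

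> No in-range aggression score is deleted as an outlier in the main analysis. The fence is applied to the total score, using one set of quartiles pooled over arms and computed without reference to arm. Totals beyond the fence are set to the fence value and kept in the GLM of 9.1. This rule, and how the total is formed for non-drivers and skipped items, is fixed before outcome data are accessed. Sensitivity analyses: (a) all scores kept, unaltered; (b) totals beyond the pooled fence excluded, with the number removed per arm reported.

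Say that this takes the place of the open transformation sentence in 9.1 for this outcome. The rule for forming the total is needed because Appendix F gives none, asks whether the volunteer drove at all, and 10.6 says that "volunteers may skip any question they do not wish to answer on surveys without affecting payment". The completer definition in 3.2 ("with at least 60% of the stems completed correctly and participating at both T1 and T2") and the exclusion for more than 15% missing data are unchanged.

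A log transformation named in advance, with everyone kept, is an acceptable alternative main rule. With an unweighted 21-item sum the minimum is 21, so log(total − 20) starts at log 1 = 0. It should also be the stated fallback if the pooled IQR is zero (for example, with more than 75% of totals at the floor), since the fence would then set every total to one value. What matters is one rule, everyone kept, fixed in advance.

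Cost: SAP wording and two short sensitivity analyses. Extreme totals are pulled in, so without careless responders power is slightly below untransformed keep-all (about .83–.90 against .89–.94).

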### **9.5 Procedures for Reporting Deviations from the Original Statistical Plan**

Any deviation(s) from the original statistical plan will be described and justified in a protocol amendment and/or in the final report, as appropriate.

### **9.6 Selection of Volunteers to be Included in Analyses**

See section 9.4 for situations where volunteer data will be excluded listwise versus pairwise.

## **10 ETHICAL CONSIDERATIONS**

### **10.1 Volunteer Identification and Confidentiality**

All data are considered private and confidential, and observations, responses, and other personal data are coded so that personal identification is not possible from data entered into information systems. No PII is collected by research staff as part of the study. PI, AI, and/or other research team members will not solicit PII from volunteers. If volunteers contact the PI, AI, or other research team member in a way that reveals PII (e.g., revealing identity in an e-mail to the PI asking a question about the study), the team member will keep these communications confidential and stored in secure drives at WRAIR and/or ARL.

### **10.2 Risks to Volunteer for Participating**

The primary risks to the volunteer includes breach of confidentiality. However, breach of confidentiality is minimized due to only the MTurk handle being used. There is no perceived risk of the information lost, stolen, or compromised.

### **10.3 Benefits to Volunteers for Participating**

There are no direct benefits to the participants in this study. Participants may find some aspects of the study interesting, entertaining, and/or thought provoking. Participants may also enjoy the

good feeling that comes with knowing they contributed to science. For science, we expect that the information we learn from this research will help guide the development of tools to help improve people's lives.

#### **10.4 Precautions to Minimize Risks to Volunteers**

Volunteers will be told during the informed consent process that they may withdraw or refuse to complete portions of the study for any reason without penalty. Participants will be given the contact information for the Principal Investigator and WRAIR HSPB to contact should they have any questions related to the experiment.

#### **10.5 Risks to Study Personnel**

There are no anticipated risks to study personnel.

#### **10.6 Financial Incentives to Volunteers**

Volunteers will be paid up to \$5 for their participation in this study. All volunteers who complete time-point one of the study will receive \$3 and volunteers will receive an additional \$2 if they complete time-point two of the study. This rate is standard pay for MTurk work (See Hitlin, 2016). Most MTurk tasks pay 10 cents or less and result in less than an equivalent hourly wage of \$5. Volunteers will not be paid for participation in a time point if they do not complete an entire time point (i.e., progress through each activity/survey and reach the end screen; volunteers may skip any question they do not wish to answer on surveys without affecting payment). If a volunteer is terminated from the study as a result of website, server, or study program related failures (e.g., server goes down during study), they may request payment by contacting the PI directly. The PI will ask Volunteerscience.org to verify that the server/website failure had occurred and if so to pay the volunteer. The approval authority of such requests is the PI. Volunteerscience.com will track the performance of each volunteer using their MTurk handle and calculate compensation appropriately without sharing any PII (including MTurk handle) with ARL or WRAIR staff.

#### **10.7 Distribution of Volunteer Payments**

Payment is made to participants via their MTurk account.

### **11 ADMINISTRATIVE PROCEDURES**

#### **11.1 Access to Source Data / Documents**

The investigators and study staff (e.g., research assistants), members of the WRAIR HSPB, representatives of the U.S. Army, USAMRMC, DoD, and other government agencies are authorized access to the study data as part of their duties and part of their responsibility to protect human volunteers in research.

## 11.2 Information Assurance and Operational Security

### 11.2.1 Information Assurance

Data collection will utilize the platform volunteerscience.com; during data collection period, the data will be stored on Amazon Web Services servers. Data/responses from participants are always uploaded to the experimental web page using secure, encrypted Secure Socket Layer (SSL) technology, which protects data using both server authentication and data encryption, ensuring that data are safe, secure, and available only to ARL AI's using valid login credentials for the account. ARL staff will download data and provide to WRAIR staff. The PI will maintain the data on secure MPB network drives.

**All AWS servers located within the USA are authorized by the Federal Risk and Authorization Management Program (FedRAMP) and the Defense Information Systems Agency (DISA)** for storage of federal government (including DoD) data at the moderate impact level (some sites are also authorized for high impact level data). Moderate impact level authorization allows storage of data where the loss of confidentiality, integrity, and availability would result in serious adverse effects on an agency's operations, assets, or individuals.

Physical access to buildings containing AWS servers is strictly controlled both at the perimeter and at building ingress points by professional security staff utilizing video surveillance, intrusion detection systems, and other electronic means. Authorized staff must pass two-factor authentication a minimum of two times to access data center floors. All visitors and contractors are required to present identification and are signed in and continually escorted by authorized staff.

Amazon facilities are equipped with fire detection and suppression equipment, multiple backup power systems, and climate and temperature control. Servers are decommissioned and disposed using processes that prevent unauthorized access to data.

The servers reside behind high-availability firewalls and are monitored using Amazon's proprietary systems for detection and prevention of various threats including denial of service, man in the middle, IP spoofing, port scanning, and packet sniffing. Automated network security audits are conducted to the standards and requirements of the SANS/FBI security test, the U.S. Department of Homeland Security's published recommendations and the Payment Card Industry Data Security Standard.

The PI will monitor volunteerscience.com for any notifications regarding security breaches and/or potential security breaches. In the event of a security breach, this will be considered a major deviation (see Section 11.4.1).

Upon the completion of data collection, all data will be downloaded via .csv files (or equivalent) and deleted from AWS servers. At the completion of the study, ARL staff will download data from Volunteerscience.com without any PII (or MTurk handles-Volunteerscience.com replaces these with new random alphanumeric) and provide the data to WRAIR staff. The PI will maintain the data on secure MPB network drives. This study meets ARL's IMD standards and requirements.

